- C. Identify baseline predictors of responsiveness to each intervention and the mechanistic basis for each treatment. Candidate predictors are (a) demographic variables (e.g., sex, age, race, ethnicity, education); (b) clinical history variables (e.g., FI frequency, volume, duration, and association with urgency and diarrhea); and (c) baseline pelvic floor physiology (e.g., anal canal resting pressure, squeeze pressure, duration of squeeze, rectal sensory threshold for first sensation and urgency, maximum tolerable volume, structural integrity of anal sphincters assessed by ultrasound, and integrity of the pelvic floor innervation by trans-sacral and trans-lumbar magnetic evoked potentials).

- D. Evaluate treatment combinations. Patients who do not meet the responder criterion by 3 months follow up will be offered the option of choosing additional therapy. This constitutes a pragmatic clinical trial which mimics clinical practice and will provide preliminary data for a future study. A second reason for allowing patients to add an additional preferred treatment if they do not show at least a 75% improvement is to facilitate recruitment; in our feasibility survey, subjects told us that the opportunity to try another treatment if the first failed would increase their willingness to be randomized. Data analysis will estimate 95% confidence intervals for the percent of responders to each treatment combination and to each monotherapy, and differences in responder rates between groups will be assessed.
  - Research objective 4. To compare the improvement in FI after combination treatment versus monotherapy and compare improvement among various treatment combinations, up to 24 months after administration of each treatment combination, compared to monotherapy.
  - Research objective 5. To estimate differences in the magnitude of improvement in FI from baseline to end of treatment between the treatment combinations.
- E. Assess the efficacy and durability of enhanced medical treatment and identify patient characteristics that predict treatment response.
  - Research objective 6. To estimate the responder rate during the last two weeks of enhanced medical treatment and also during follow up at 3, 6, 12, and 24 months.
  - Research objective 7. To assess the proportion of patients reporting AEs of pelvic pain of grade II or higher, or SAEs requiring hospitalization, during all weeks of medical treatment.

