It could be argued that, even if BIO were to be equally effective as INJ of dextranomer, it would be logical to try BIO first because it is safer, and to only use INJ in those who fail BIO. In practice, however, there is no consistent standard for defining BIO or judging what "failing biofeedback" means. If the proposed comparative effectiveness study shows that BIO is equally effective or more effective than INJ, treatment algorithms and insurance reimbursement policies may need to be re-evaluated. An outcome such as this might also stimulate research into whether treatment combinations may be more consistently effective than trying these treatments one at a time.

An NIDDK Workshop hosted in 2014 addressed research priorities for FI and concluded that the highest priority for research should be "trials comparing the effectiveness, safety, and cost of current therapies". Such a comparative effectiveness study needs to be performed at multiple sites because (1) the number of patients currently referred for these treatments is relatively small at individual medical centers, (2) FI is a multi-faceted disorder and patient phenotypes may differ among centers, and (3) the success of BIO varies across clinical settings and is known to be influenced by the training and experience of the therapist.

Outcome Domain	BIO	INJ	SNS	
Efficacy (success rated by authors' definition)	55%  - 93% 	53% 	83% 	
Efficacy (>75% decrease in FI frequency)	78% 	32% 	56% 	
Continence (%)	5%  - 44% 	5.9% 	25%  - 40% 	
Adverse events (pain or infection)	0% 	10% 	6%  -11% 	
Reimbursement (range in US \$)	\$1,235 – 2,300	\$3,000 - 7,408	\$29,000 - 69,000	

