### 3.0 Study design:

The overall study design, shown in Figure 1, is an unmasked, multisite, randomized, parallel group study comparing the effectiveness of two treatments for moderate to severe FI. This study design builds on the core recommendations of the NIDDK Workshop for design of an ideal comparative effectiveness RCT. It is a parallel group design which has the following features:

- 1. *Baseline:* Patients will keep a daily symptom diary for two weeks prior to the Baseline visit to (a) document that they meet the minimum frequency required for inclusion in the study and (b) provide a reference value for assessing treatment response at the end of EMM and at 3, 6, 12, and 24 months follow-up points. Adverse events and cost will be reassessed at each in-person visit and at 3-, 6-, 12-, 18- and 24-month follow up assessments.
- 2. Enhanced medical management: All patients meeting inclusion criteria will first be treated with EMM for 4 weeks to identify those who really need a more expensive and more invasive treatment. The key components of treatment are patient education about the basic physiological mechanisms for defecation, diet and medication to normalize stool consistency, and pelvic floor exercises taught by printed instructions. (Section 6.1) Additional goals of the EMM protocol are (a) to ensure that patients randomized to INJ meet the accepted criteria by failing to respond to EMM, and (b) to document the efficacy and the durability of systematically applied, optimized EMM. This design is similar to the one used in the Heymen RCT which provides the strongest evidence for the efficacy of BIO. We believe the exclusion of patients

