### 4.0 Outcome Measures

4.1 Primary Outcomes: There are three primary outcomes: efficacy, safety, and cost.

*4.1.1 Efficacy:* The primary efficacy analysis will be based on the proportion of responders in each treatment arm. A responder will be defined as an individual whose symptom diaries demonstrate at least a 75% reduction in the average weekly frequency of FI from baseline (prior to the EMM to the last two weeks of the treatment period preceding the 3-month post intervention follow up. The rationale for choosing a 75% reduction in the frequency of staining, solid and liquid stool incontinence as the primary outcome measure is that, both in focus groups and surveys we conducted, half of patients with FI reported that they did not consider a 50% reduction in FI episodes to be a satisfactory measure of treatment success; rather, they believed an improvement of 70-80% was necessary for a treatment to be considered successful.

The frequency of FI will be recorded on a paper diary. Patients will be asked to record (1) the time of each accidental bowel leakage (ABL), (2) the amount of leakage that occurred, (3) the rectal sensation that occurred prior to the event (no awareness, normal warning, or strong urge), and (4) the consistency of the leaked stool. Patients will also be asked to record (5) the time of any BM that occurred in the toilet even if this starts as an ABL and is finished by passing stool in the toilet, (6) the consistency of the BM using the Bristol Stool Form Scale, and (7) medications or other treatments employed. The primary outcome is based only on the number of FI events; however, the amount of stool lost and the type of sensation experienced before the leakage are needed to guide the BIO intervention, and the number and consistency of BMs and use of fiber or medications is used to guide the EMM intervention. Rather than use different diaries for each of these purposes, we will ask all subjects to use this paper diary throughout the intervention period and for two-week periods preceding all follow up assessments.

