Previous studies have identified a number of limitations to paper diaries: (1) Missing data if subjects forget to complete the diary or if it is illegible. (2) Inaccurate data that may result if subjects forget to record events when they occur and then try to remember what happened at the end of the day or several days later. In previous studies, we provided patients with a pocket-sized paper diary to take with them throughout the day and asked them to transfer their symptom ratings from the paper diary to a website at the end of the day. If they failed to submit a report to the website within 12 hours, they were sent an email reminder or were telephoned. They were also reminded the next time they attempted to enter data, if the data for the previous day was missing, and they were given an opportunity to report on the previous day; however, they were not permitted to go back further than the previous 24 hours. They were also provided with bonus payments for not missing any diary reports. With this combination of techniques, we were able to obtain an average of 73 consecutive days of symptom diaries without interruption from 185 IBS patients varying in age from 18 to 84. However, there is concern that since advancing age is a risk factor for FI, the patients who enroll in this study will be older and less comfortable than young or middle-aged subjects with transferring data to the internet. Therefore, to avoid biasing enrollment against these older subjects, we decided to use paper diaries for this study. To ameliorate potential problems with missing or untimely data reporting we will (1) thoroughly train subjects in recording their diary information at enrollment, and (2) telephone subjects during the first two weeks that they keep the diary to ensure that they are able to record events on this paper diary when they occur.

To protect against experimenter bias, patients will be classified as responders or non-responders based on diary data entered into the electronic data capture (EDC) system at the end of EMM and at 3-, 6-, 12-, and 24-month follow-up. Once the diary data are entered, a calculation performed within the EDC system will determine which patients are non-responders eligible for randomization, and the same process will determine which patients are non-responders at 3 months so they can be offered alternative treatment.

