#### 8.3 Analysis of Secondary Aims

*Identify predictors of treatment response to each intervention.* Generalized linear modeling will be used to identify baseline variables which are significant independent predictors of responder status at 3 months. Candidate independent variables in these models include (a) demographic variables (e.g., sex, age, race, ethnicity, education); (b) clinical history variables (e.g., FI frequency, volume, duration, and association with urgency and diarrhea); and (c) baseline pelvic floor physiology (e.g., anal canal resting pressure, squeeze pressure, duration of squeeze, rectal sensory threshold for first sensation and urgency, maximum tolerable volume, structural integrity of anal sphincters assessed by ultrasound, and integrity of the pelvic floor innervation by trans-sacral and trans-lumbar magnetic evoked potentials) and other moderator variables described in the protocol. Differences in predictors of response among the treatment groups will be assessed by evaluating interaction terms for the predictors and treatment group. Secondary analyses evaluating predictors of treatment response at other time points and predictors of other secondary outcomes will be conducted using similar methods.

Investigate the mechanistic basis for treatment success for each intervention. General linear modeling will be used to identify measures associated with change from baseline to 3 months in FI frequency. The independent variables to be tested are anal squeeze pressures, rectal sensory thresholds, rectal maximum tolerable volume, trans-lumbar and trans-anal magnetic evoked potential, stool consistency measure by the Bristol Stool Form Scale, and adherence to protocol. Differences in predictors among the treatment groups will be assessed by evaluating interaction terms for the predictors and treatment group.

*Evaluate treatment combinations.* To assess the effectiveness of allowing non-responders to choose an additional treatment at 3 months, we will estimate 95% confidence intervals for the number of responders in each treatment-order combination at 6, 12, and 24 months using a Wilson Score interval. Confidence intervals will be compared descriptively.

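### Aim D uses one two-week diary with the same 75% cut-off and baseline to define both 3-month failure and later combination response, so some apparent response to an added treatment is regression to the mean, and unequally so between sequences

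*Combined protocol and SAP*

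**What the plan says.** **Response rule.** Section 4.1.1 defines a responder by "at least a 75% reduction in the average weekly frequency of FI from baseline", the baseline being the diary kept before enhanced medical management (EMM). Diaries are kept "for two-week periods preceding all follow up assessments".

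**Entry to Aim D.** Section 1.1, Aim D: "Patients who do not meet the responder criterion by 3 months follow up will be offered the option of choosing additional therapy". Section 4.1.1 leaves the decision to a calculation in the data capture system: after describing how EMM non-responders are identified, it adds that "the same process will determine which patients are non-responders at 3 months so they can be offered alternative treatment".

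**Later response.** Section 3.0, item 1, says the baseline diary will "provide a reference value for assessing treatment response at the end of EMM and at 3, 6, 12, and 24 months follow-up points". Section 8.3 gives no separate definition of response to a combination. It plans Wilson intervals: "we will estimate 95% confidence intervals for the number of responders in each treatment-order combination at 6, 12, and 24 months". Section 1.1 adds that "differences in responder rates between groups will be assessed", and research objective 4 compares combinations with each other and with monotherapy.

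**Status.** Section 5.4 calls these comparisons exploratory on grounds of power, and Section 8.3 compares the intervals descriptively. The Synopsis allows a second two-week baseline diary for patients whose FI varies. There is no matching provision at 3 months.

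**The concern.** A two-week count is a noisy measure of a patient's underlying FI rate. Selecting patients because one such count fell on the wrong side of a line, then scoring them with a fresh count against the same line, guarantees some crossings without any change in the patient. This is regression to the mean. With no randomized or untreated comparator among the non-responders, those crossings cannot be separated from benefit of the added treatment.

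Two consequences follow. First, the combination response rate overstates what the added treatment did. Second, the overstatement differs by first treatment. If 78% of an arm respond, its failures tend to lie closer to the line than the failures of an arm where 32% respond. Sequences starting with biofeedback (BIO) could therefore look better than those starting with injection (INJ) when no added treatment has any effect. The monotherapy comparator is selected in the opposite direction: the flow in Section 5.4 has essentially every 3-month non-responder choosing an added treatment, so those left on monotherapy are essentially the 3-month responders. Wilson intervals describe sampling error only.

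**Working it through.** **1. The plan's own figures reproduce.** Section 5.4 expects 78 BIO and 92 INJ patients assessed at 3 months, with response of 78% and 32%. Non-responders: 78 × (1 − 0.78) = 17.2 and 92 × (1 − 0.32) = 62.6, matching 17 and 63 in Table 7. With an equal split over two options, this is about 8-9 per BIO-first sequence and 31-32 per INJ-first sequence. Table 8's Wilson intervals also reproduce (n = 10 at 50%: 24-76%; n = 50 at 90%: 79-96%).

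**2. How many failures lie near the line?** From Table 3 (≥50% and ≥75% reduction):
- BIO: (93 − 78)/(100 − 78) = 15/22 = 68% of failures are between 50% and 75%.
- INJ: (53 − 32)/(100 − 32) = 21/68 = 31%.

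**3. Expected response with an inert added treatment, threshold model.** Assume the 3- and 6-month results follow a bivariate normal with correlation ρ and an unchanged response rate p in the arm. With t = Φ⁻¹(1 − p), the probability of response at 6 months given failure at 3 months is 1 − Φ₂(t, t; ρ)/(1 − p).

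| ρ (assumed) | BIO, p = 78% | INJ, p = 32% | Gap | p = 60% | p = 40% | Gap |
|---|---|---|---|---|---|---|
| 0.5 | 55% | 22% | 33 | 40% | 27% | 13 |
| 0.7 | 42% | 17% | 25 | 31% | 20% | 10 |
| 0.8 | 34% | 13% | 21 | 25% | 17% | 8 |
| 0.9 | 24% | 9% | 15 | 17% | 12% | 6 |

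The 60%/40% columns are the difference Section 5.2.1 is powered for: 20 points around an average of 50%.

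**4. The same question from simulated diary counts.** Assumptions: at least 4 episodes in the baseline diary; mean baseline 3.4 (BIO) and 4.8 (INJ) episodes a week, borrowing Table 3's FI days per week, or 7 as a sensitivity; between-patient CV 0.62; Poisson or overdispersed (negative binomial) counts; a logit-normal spread of true remaining FI, calibrated to 78% and 32%.
- Poisson, spread SD 1 / 1.5 / 2 / 3: BIO 51 / 41 / 34 / 26%; INJ 20 / 16 / 13 / 10%.
- All settings: BIO about 20-71%, INJ about 8-28%.

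**5. Fitting both Table 3 rates narrows the range.** A beta distribution of true reduction, fitted to the ≥50% and ≥75% rates with 4 episodes a week at baseline (CV 0.6), gives 44 / 48 / 51% after BIO and 13 / 15 / 18% after INJ, for Poisson and negative binomial counts with k = 10 and k = 5. Varying the baseline and overdispersion gives about 34-59% and 11-26%, with a gap of about 19-39 points. A count model at 60%/40% gives 28-30% against 15-20%, a gap of 10-13 points.

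**6. What lowers these rates.**
- Waning: raising FI by an illustrative 20% after 3 months takes the Poisson figures from about 47% to 38% (BIO) and 15% to 10% (INJ).
- Missing diaries: Section 8.3 does not say how they are handled in this analysis. If they count as non-response, 15% attrition to 12 months takes 44-51% to 0.85 × 44 = 37% and 0.85 × 51 = 43%.

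**7. What candidate remedies achieve.**
- Stratifying by the 3-month percent reduction cut the simulated gap by about 20-36%.
- Requiring ≥75% on two later diaries, in the model of step 5, leaves 26-32% after BIO and 5-6% after INJ. The absolute gap narrows, but in the Poisson case the ratio rises from 0.436/0.130 = 3.4 to 0.264/0.054 = 4.9. Confirmation alone does not make the sequences comparable.

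**The case against.** The strongest reply is that Aim D is already modest: labelled exploratory, compared descriptively, intended to inform a future study, and framed in Section 8.3 as a pragmatic question about letting non-responders choose another treatment. With groups this small (4 of 9 has a Wilson interval of 19-73%), nobody should rank sequences firmly. Research objective 5 and the severity and quality-of-life analyses by combination do not use the 75% cut-off. All of this limits the consequences. None of it removes the problem: the exploratory label answers low power, not bias, regression to the mean can also affect the continuous measures, and Section 1.1 still intends to assess differences in responder rates.

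The reply is stronger on size. A reader might infer that an inert added treatment would show 44-51% response after BIO and 13-18% after INJ, with a spurious gap of about 30 points. The documents do not support those as findings. They give neither within-patient diary variability nor 3-to-6-month persistence, and the 78% and 32% come from two separate trials, a kind of comparison Section 2.1 itself warns about. At the planned 20-point difference the gap is far smaller.

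A reader might also infer that every combination should have to be confirmed at 6 and 12 months. That is debatable. Follow-up is timed from the first randomized treatment. Under Section 3.1 the 3-month visit may be 3 weeks late and the added treatment may start up to 4 weeks after it, so the 6-month diary can precede completion of that treatment and score real benefit as failure.

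**Conclusion.** The design point holds. The same single-diary cut-off and baseline select the failures and score the later response, with no confirmation and no control among the non-responders. Combination response rates will include chance crossings, more of them after the arm with the higher 3-month rate.

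The size is an assumption, not a result: roughly 20-70% after BIO and 8-28% after INJ at 78%/32%. The gap is about 20-40 points in models fitted to both Table 3 rates (smaller if persistence is high, for example 15 points at ρ = 0.9), and about 8-13 points at 60%/40% for ρ of 0.5 to 0.8. These figures assume a stable true FI rate after 3 months and complete later diaries; waning, or counting missing diaries as non-response, lowers the rates.

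It would be wrong to extend this to the main efficacy results. The primary comparison is randomized, and the long-term intention-to-treat analyses keep 3-month failures as non-responders, so neither is affected.

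**What to change.** Change the analysis text for Aim D and Section 8.3 only:

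1. When treatment-order combinations are compared, present results stratified by, or adjusted for, the percent reduction on the 3-month diary, which is already collected. Report change from the 3-month level beside the 75% rate.
2. State that single-diary combination response rates include regression to the mean, that adjustment removes only part of it, and that the rates are not to be read as the effect of the added treatment or used to rank BIO-first against INJ-first sequences. State also how missing diaries are handled in this analysis.
3. As a sensitivity analysis only, show response confirmed on two later diaries, for example at 12 and 24 months, because the 6-month diary may precede completion of the added treatment.

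The cost is SAP wording and a little programming, with no new data. The downside is imprecision: with about 8-9 patients per BIO-first sequence, stratified figures will be rough. The confirmed rate will be lower and will lose patients to attrition (15% planned from 3 to 12 months and a further 15% to 24 months).

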## 5.3. Secondary Aim to Evaluate Treatment Combinations

A secondary aim of the study is to evaluate treatment-order combinations after participants are allowed to cross over into other study arms. At the 3-month assessment, non-responders to randomized treatment can choose to initiate an additional treatment. This is a pragmatic approach reflecting the reality that patients in clinical care who are not happy with their initial FI treatment may choose to try another treatment. Table 7 shows the number of 3-month non-responders in each randomization group who are expected to be followed to 6, 12 and 24 months with the assumption of 15% attrition (loss to follow up or missing outcomes for other reasons) between the 3- and 12-month assessments and an additional 15% attrition between the 12- and 24-month assessments. Since non-responders can choose to try the other study treatment or SNS after 3 months, we estimate that between 5 and 50 participants will be in each of the possible treatment-order combinations at 6, 12 and 24 months. We will estimate 95% confidence intervals for the number of responders in each treatment-order combinations at 6, 12 and 24 months. We will estimate 95% confidence intervals for the number of responders in each treatment-order combinations at 6, 12 and 24 months. We will estimate 95% confidence intervals for the number of responders in each treatment-order combinations at 6, 12 and 24 months. We will estimate 95% confidence intervals for the number of responders in each treatment-order combination at each time point. Table 8 shows 95% confidence intervals for a range of group sizes and responder percentages; confidence intervals are estimated using a Wilson Score interval recommended for small sample sizes.

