#### 5.4 Estimated patient flow for this study

Figure 3 shows the estimated flow of patients through this study and identifies our assumptions regarding attrition. We estimate we will need to screen 855 patients because 2/3 will be ineligible or unwilling to be randomized. This leaves 285 to be recruited into the EMM protocol. Based on the Heymen study, we assume

15% attrition during this treatment phase and also assume that 20% (n=57) will be responders to EMM and therefore not eligible for randomization. This will leave 194 to be randomized (97 per group).

Figure 3 shows that we expect 78 from the BIO group to complete the 3-month assessment after allowing for attrition of 20% and we expect 92 from the INJ group to complete the 3-month assessment. (We assume attrition will be no greater than 5% for the INJ group because this is a low-burden treatment and also because patients will want to be screened for AEs related to INJ.) However, the statistical analysis will be by intent to treat (ITT) and will include all 194 randomized to treatment; patients who are lost to follow up prior to 3 months will be considered treatment failures. The number of patients we expect to be responders to each of the treatments at the 3-month assessment is based on the pivotal trials shown in Table 1. We separated them in this way in Figure 3 to be able to estimate the numbers of non-responders who are likely to choose an additional treatment option after 3 months. The expected number of non-responders eligible for an additional therapy at 3 months is 63 for the INJ arm^16 and 17 for the biofeedback arm^15. Assuming equal probability of choosing either of the 2 available options as an added or alternative treatment, we could expect 40 patients to choose the SNS treatment, 32 to choose BIO, and 9 to choose INJ. For the primary analyses of follow up at 6, 12 and 24 months, these non-responders will be retained in the ITT analysis as non-responders to their primary assignment at randomization. However, when we perform exploratory analyses of treatment combinations, these subjects will be treated as distinct groups and compared to patients who received monotherapy for the duration of the study. These comparisons (Aim D) are exploratory because there is insufficient power to test for significance. The left column of boxes in Figure 3 shows how we intend to follow up the responders to EMM.

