#### 8.2 Analysis of Secondary Efficacy Endpoints

Assessment of Efficacy through 24 months. Treatment response (≥75% reduction in weekly FI episodes) at time points through 24 months will be analyzed using a longitudinal extension of the model used for the primary efficacy analysis. Month of assessment, and interaction between month and other predictors, will be included in the model, and the correlation between measures assessed on the same participant over time will be modeled using an appropriate covariance structure. Participants classified as non-responders at 3 months will continue to be considered non-responders at subsequent time points. Participants with missing responses will be classified as non-responders, but sensitivity analyses will be conducted to assess the impact of this assumption.

Assessment of Safety through 24 months. The percentage of participants reporting AEs of pelvic pain of grade II or greater severity, treatment site infection, or an SAE requiring hospitalization by 6, 12, 18, and 24 months will be estimated with 95% confidence intervals using the Wilson Score interval method. Separate estimates will be produced for the groups of participants treated with each of the two therapies alone, and for participants in each of the treatment-order combinations. Confidence intervals will be compared descriptively.

Assessment of Cost of Care through 24 months. The median costs per participant from the perspectives of payers, patients, and society through 24 months will be estimated for each of the treatment groups, including the treatment combinations, using methods described for the primary cost of care endpoint. No formal hypothesis testing will be done, and p-values will be presented for informational purposes only.

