Assess the efficacy and durability of enhanced medical treatment and identify patient characteristics that predict treatment response. The proportion of responders will be calculated at the end of EMM and at 3-, 6-, 12-, and 24-month follow-up. A longitudinal generalized linear model will be constructed to predict treatment response based on time and clinical site; the model will account for the lack of independence between multiple measures assessed over time on the same study participant by modeling the within-participant covariance structure. Participants who are non-responders to EMM at 3 months will continue to be classified as non-responders at 6, 12, and 24 months. Participants without a valid bowel diary will be classified as non-responders at that time point, and those who initiate off-study treatment for FI after EMM will be classified as non-responders at each subsequent visit/assessment. Using this model, we will compare response rates at the end of EMM to response rates at 3, 6, 12, and 24 months. We will also calculate 95% confidence intervals for the percentage of participants reporting AEs during EMM. Costs of EMM will be estimated and compared to costs of the other study interventions using methods described for cost of care analysis. The predictors of response to EMM at baseline, 3, 6, 12, and 24 months will be explored using generalized linear modeling.

*Cost- Effectiveness Analysis.* We will estimate the impact of each intervention on quality-adjusted life-years (QALYs). QALYs are summary measures of morbidity and mortality that typically range from 0 to 1 over a full year, where 1 represents perfect health. QALY estimates will be obtained from the EQ-5D; annual QALY measures will be calculated. We will assess the average cost per QALY gained for each intervention and the incremental cost per QALY gained by comparing the interventions ordered from lowest to highest QALY gains (i.e., comparing the intervention with medium effectiveness to the intervention with lowest effectiveness and the intervention with highest effectiveness to the intervention with medium effectiveness).

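### The EMM durability analysis counts every missing follow-up diary as lost response and plans no sensitivity analysis, so attrition alone can produce an apparent loss of benefit

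*Combined protocol and SAP*

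**What the plan says.** The paragraph of section 8.3 on the efficacy and durability of enhanced medical treatment (Aim E) sets these rules:

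- Missing diary: "Participants without a valid bowel diary will be classified as non-responders at that time point".
- Carry-forward: "Participants who are non-responders to EMM at 3 months will continue to be classified as non-responders at 6, 12, and 24 months".
- Starting off-study treatment for FI after EMM counts as non-response from then on.
- Contrast: "Using this model, we will compare response rates at the end of EMM to response rates at 3, 6, 12, and 24 months". The model is a longitudinal generalized linear model with time and clinical site.

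The paragraph names no sensitivity analysis, significance level or analysis set.

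The randomized arms get the same coding with a safeguard. For response through 24 months, section 8.2 says: "Participants with missing responses will be classified as non-responders, but sensitivity analyses will be conducted to assess the impact of this assumption". Section 8.1 makes a similar commitment for the primary efficacy analysis. Neither is extended to EMM.

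On numbers, section 5.4 says "This leaves 285 to be recruited into the EMM protocol" and assumes "15% attrition during this treatment phase and also assume that 20% (n=57) will be responders to EMM". The only long-term attrition rates in the readable text are in section 5.3: "15% attrition (loss to follow up or missing outcomes for other reasons) between the 3- and 12-month assessments and an additional 15% attrition" from 12 to 24 months. They are stated for 3-month non-responders to randomized treatment.

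**The concern.** In a comparison of two randomized arms, coding missing as failure acts on both sides, and its effect on the contrast depends on how far missingness differs between arms. The EMM contrast sets one cohort against its own earlier value. Every EMM responder whose later diary is absent becomes a coded loss, and the rule has no counterpart that raises a later rate. Participants who drop out during EMM are already non-responders at the reference point, so they do not add to the fall.

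The carry-forward rule can add to this. It is needed for observed relapse at 3 months, because those participants may then be randomized. But it does not separate observed from coded non-response, so one missed 3-month diary can become failure at every later visit.

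Missing late diaries are foreseeable. Section 4.1.1 lists missing entries as a known limitation of paper diaries, and its stated remedies are training at enrollment and telephone calls in the first two weeks of diary keeping.

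At stake is what Aim E can conclude. The trial could report that the benefit of EMM wanes when part or all of the decline is absent diaries.

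**Working it through.** **Reproducing the plan's figures.** Table 7, INJ: 63 × 0.85 = 53.6 (stated 53) and 63 × 0.85² = 45.5 (stated 45). BIO: 17 × 0.85 = 14.5 (stated 15) and 17 × 0.85² = 12.3 (stated 13). The 15% + 15% reading is therefore right. EMM responders: 0.20 × 285 = 57, as stated. However, 285 − 43 − 57 = 185, whereas the planned 194 randomized equals 285 × 0.85 × 0.80 and implies 0.20 × 242 ≈ 48 responders. Both 57 and 48 are run below.

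**Assumptions that the plan does not supply.** (a) EMM responders are lost at the section 5.3 rates. (b) No responder relapses. (c) Two-sided alpha is 0.05.

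**Built-in fall, 57 responders.**

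- 12 months: 57 × 0.85 = 48.5, so about 48 are still coded as responders (85%), with 8–9 missing.
- 24 months: 57 × 0.85² = 41.2, so about 41 (72%), with 15–16 missing. Cumulative loss is 1 − 0.7225 = 27.75%.
- As a share of all 285: 20.0%, then 17.0%, then 14.45%.

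**How much of this is bias.** If m is the proportion of responders with a missing diary and f is the share of those who in fact still respond, the bias is m × f. At 24 months, f = 1 gives 27.75 points among responders. If half have relapsed it is 27.75 / 2 = 13.9 points, and if all have relapsed it is zero.

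**When it would look significant.** With no relapse, all discordant pairs run one way, so the exact two-sided McNemar p is 2 × 0.5^d for d missing responders: d = 3 gives 0.25, d = 5 gives 0.0625, d = 6 gives 0.031. Six is the threshold (10.5% of 57; 12.5% of 48).

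| Case | Missing | Exact p | Logit GEE p |
|---|---|---|---|
| 57 responders, 12 months | 8–9 | 0.008–0.004 | 0.002 |
| 57 responders, 24 months | 15–16 | 0.00006–0.00003 | 0.00004 |
| 48 responders, 12 months | 7–8 | 0.016–0.008 | 0.010 |
| 48 responders, 24 months | 13–14 | 0.0002–0.0001 | 0.0004 |

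The GEE used time and site, exchangeable working correlation and robust standard errors. Its analysis set was everyone starting EMM (285) for the 57-responder rows and EMM completers (242) for the 48-responder rows.

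The chance of six or more missing responders, treating the number missing as binomial, depends on cumulative loss:

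| Cumulative loss | 57 responders | 48 responders |
|---|---|---|
| 5% | 6.5% | 3% |
| 10% | 51% | 35% |
| 15% | 87.5% | 75% |
| 20% | 98% | 94% |
| 27.75% | >99.9% | 99.7% |

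**Same scenario with missing diaries left missing.** There are no discordant pairs: every responder with a diary is still responding at each visit. The whole apparent decline comes from the coding.

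**The case against.** A reader might infer that ordinary attrition will make EMM appear to fail at a significant level. The documents do not support that, for four reasons, all of which stand:

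- The 15% + 15% rates belong to non-responders to randomized treatment. EMM responders have improved and face no further procedure. Section 5.4 says that Figure 3 sets out the attrition assumptions and the follow-up of EMM responders, and that figure is not available here.
- Research objective 6 is to estimate responder rates, and section 8.3 gives no alpha or decision rule for this contrast. Bias in the estimate is therefore the better measure of the problem. It should be noted, though, that section 8.2 marks several other secondary p-values as informational, and the EMM paragraph carries no such caveat.
- No relapse is the extreme case. The plan expects some relapse and provides a randomization route for it. A missing participant who has relapsed is coded correctly.
- At about 5% cumulative loss, 2–3 of 57 are missing and the exact p is 0.25–0.5.

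A second tempting reading is that the rule is simply wrong and missing at random should replace it. That does not follow either. Treating missing as failure is a recognized conservative convention, used consistently in this plan. If people whose EMM has stopped working are likelier to stop returning diaries, missing at random would overstate durability.

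What the objection does not remove is the direction of the bias or the absence of any check on it.

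**Conclusion.** The concern holds as a cheap improvement to a secondary aim; the primary efficacy, safety and cost analyses are untouched. The rule as written biases the EMM durability estimate downward whenever a missing participant still responds, and section 8.3 gives no means of seeing by how much. The size depends on unknown attrition and relapse: from nothing, if all the missing have relapsed, to about 28% of the response at 24 months, if none has and the section 5.3 rates apply. Carrying forward missed 3-month diaries could add to this. Six or more missing responders could pass for a significant loss at an assumed two-sided 0.05; about 5% cumulative loss would not. These conclusions are the same with 48 or 57 responders.

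**What to change.** In the EMM paragraph of section 8.3:

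1. Add a pre-specified analysis that leaves missing diaries missing, using a longitudinal likelihood model or multiple imputation under missing at random. Report it beside the current rule, and label the current rule the lower bound.
2. At each visit, report coded non-responders in three groups: observed relapse, off-study treatment and missing diary.
3. In the added analysis, apply the 3-month carry-forward only to non-response observed on a diary.
4. Base any statement that EMM benefit wanes on both analyses. State the analysis set. If it is EMM responders only, report the proportion retaining response with a confidence interval, because response at the end of EMM is then 100% by definition and a logit contrast against it cannot be estimated.

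The cost is SAP wording, one more model and one table, with no new data and no change to visits or treatment. The downside is that the added model relies on missing at random and may overstate durability if relapsers stop returning diaries, which is why the current rule should stay beside it.
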